### 5.2.11 Unscheduled Visits

Scheduled visits, unscheduled visits, and repeat assessments will be considered for any analysis of the patient's worst or maximum post-Baseline grade. For all other safety analyses, when summarizing post-Baseline visits, only data collected at scheduled visits will be tabulated. Unscheduled visits and repeat assessments will be excluded. All collected data (scheduled, unscheduled, or repeat) will be presented in the listings.

QMD Ref: Worldwide-TMP-ST-054-1.0_Effective: 12Aug2022	Governing QMD: Worldwide-SOP-ST-026
Confidentiality Statement	

This document is the property of Worldwide Clinical Trials Inc. and may not be duplicated, copied, altered or removed from company without prior approval from Worldwide Quality Assurance or in compliance with Worldwide Standard Operating Procedures.

Worldwide Clinical Trials Controlled Quality Management Document			
 WORLDWIDE CLINICAL TRIALS	Sponsor:	Flamingo Therapeutics	
	Protocol Number:	FLM-6774-201	
STATISTICAL ANALYSIS PLAN			

### 5.3 Randomization Strata

Randomization will be stratified by Eastern Cooperative Oncology Group (ECOG) performance status (0 vs 1) for patients enrolled under the original protocol or Amendment 1. For patients enrolled under Amendment 2 or later, randomization will be stratified by CPS ( $1 \leq \text{CPS} < 20$  vs  $\text{CPS} \geq 20$ ). The change in stratification variables will not impact the intended overall randomization balance.

A TPS value  $\geq 30$  may be used for initial eligibility. The subject will be assigned to the  $1 \leq \text{CPS} < 20$  stratum, if  $30 \leq \text{TPS} < 50$ , or the  $\text{CPS} \geq 20$  stratum, if  $\text{TPS} \geq 50$ . However, a CPS value must be obtained and reported utilizing a tissue sample obtained prior to the start of study treatment.

### 5.4 Reporting Conventions

All CDISC submission datasets, data listings, summaries, figures, and statistical analyses will be generated using SAS version 9.4 or higher.

Summaries will be presented by treatment arm and a cumulative overall column. Treatment arm labels will be displayed as follows.

Danvatirsen + Pembrolizumab (N=XX)	Pembrolizumab (N=XX)	Overall (N=XX)
---------------------------------------	-------------------------	-------------------

Danvatirsen + Pembrolizumab = Danvatirsen 2 mg/kg or 3 mg/kg + Pembrolizumab 200 mg IV  
Pembrolizumab = Pembrolizumab 200 mg IV

Table summaries will present patient by either planned or actual treatment assignment, as specified in the Statistical Analysis Plan. In the rare case that a subject is mis-randomized or administered the incorrect treatment, actual treatment assignment is defined as the treatment the patient received for the majority of the study.

Unless otherwise stated, listings will be sorted in the following order: Treatment arm, Subject ID, Start Date, End Date, and Parameter.

Continuous variables will be summarized by the number of non-missing observations, mean, median, standard deviation, and minimum and maximum. Summaries of change from Baseline values will only include patients with a values at both baseline and the post-baseline time-point.

Categorical variables will be summarized by presenting the frequency and percent. Percentages will be based on the number of patients in the column header unless otherwise specified in the footnote. For each variable, all categories will be shown. Zero frequencies (but not the percent) within a category will be presented.

QMD Ref: Worldwide-TMP-ST-054-1.0_Effective: 12Aug2022	Governing QMD: Worldwide-SOP-ST-026
Confidentiality Statement	
This document is the property of Worldwide Clinical Trials Inc. and may not be duplicated, copied, altered or removed from company without prior approval from Worldwide Quality Assurance or in compliance with Worldwide Standard Operating Procedures.	

Worldwide Clinical Trials Controlled Quality Management Document		
 WORLDWIDE CLINICAL TRIALS	Sponsor:	Flamingo Therapeutics
	Protocol Number:	FLM-6774-201
STATISTICAL ANALYSIS PLAN		

Means, medians, and percentiles will be displayed to one more decimal place than the source data, dispersion statistics (e.g., standard deviation) will have two more decimal places, and the minimum and maximum will be displayed to the same number of decimal places as reported in the raw data.

Confidence Interval (CI) will be displayed in two decimal places. *p*-values will be quoted to 4 decimal places consistent with SAS PVALUEw.d format set to PVALUE6.4. *P*-values < 0.0001 will be presented as p<0.0001.

## 5.5 Patient Disposition

The number and percentage of the following will be summarized for all screened subjects.

- Patients that were enrolled
- Screen failures and the reasons for screen failure
- Patients who were randomized
- Patients who were randomized but not treated with Danvatirsen and or Pembrolizumab and reason(s) not treated
- Patients who discontinued Pembrolizumab and reason for discontinuation
- Patients who discontinued Danvatirsen and reason for discontinuation

A separate summary will be provided for the number of subjects in each analysis set.

## 5.6 Protocol Deviations

Major protocol deviations will be summarized for the Safety Analysis Set by actual treatment. The summary will include number and percentage of subjects with each deviation as well as the number of individual protocol deviations as events. Details for identification and classification of protocol deviations are outlined in the Protocol Deviation Handling Plan (PDHP).

All major and minor protocol deviations will be listed.

QMD Ref: Worldwide-TMP-ST-054-1.0_Effective: 12Aug2022	Governing QMD: Worldwide-SOP-ST-026
Confidentiality Statement	

This document is the property of Worldwide Clinical Trials Inc. and may not be duplicated, copied, altered or removed from company without prior approval from Worldwide Quality Assurance or in compliance with Worldwide Standard Operating Procedures.

Worldwide Clinical Trials Controlled Quality Management Document			
 WORLDWIDE CLINICAL TRIALS	Sponsor:	Flamingo Therapeutics	
	Protocol Number:	FLM-6774-201	
STATISTICAL ANALYSIS PLAN			

## 5.7 Demographics and Baseline Characteristics

Standard continuous or categorical variable summaries will be presented for the Safety Analysis Set based on actual treatment..

### Demographics

- Age at Informed Consent (years),
- Age Category (<65, >= 65, >= 65 to <75, >=75)
- Sex at Birth
- Fertility Status for Women
- Ethnicity
- Race

### Other Baseline characteristics

- Height (cm),
- Weight (kg),
- Tobacco History
- ECOG Performance Status (0, 1)

## 5.8 Cancer History, Surgical History, and Prior Cancer Therapy

All cancer history and prior cancer therapy summaries will be reported by actual treatment for the Safety Analysis Set. All cancer history, surgical history, and prior cancer therapy data will be listed. Systemic anti-cancer therapy data will be listed.

### Cancer History

- Tumor Details at Baseline
  - Number of Total Lesions
  - Number of Target Lesions
  - Number of Non-Target Lesions
  - Location of Metastatic Disease
- Initial Diagnosis
  - Primary Tumor Location
  - Tumor Stage
  - Histology
  - Complete Surgical Resection Performed
  - TNM Stage

QMD Ref: Worldwide-TMP-ST-054-1.0 Effective: 12Aug2022	Governing QMD: Worldwide-SOP-ST-026
Confidentiality Statement	

This document is the property of Worldwide Clinical Trials Inc. and may not be duplicated, copied, altered or removed from company without prior approval from Worldwide Quality Assurance or in compliance with Worldwide Standard Operating Procedures.

Worldwide Clinical Trials Controlled Quality Management Document			
 WORLDWIDE CLINICAL TRIALS	Sponsor:	Flamingo Therapeutics	
	Protocol Number:	FLM-6774-201	
STATISTICAL ANALYSIS PLAN			

- Current Diagnosis
  - Tumor Stage
  - TNM Stage
- HPV Status
- Combined Positive Score
- Combined Positive Score (0, >= 20, 20 - 49, >=50)
- Tumor Proportion Score
- Tumor Proportion Score (>=30, >=50)

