3 STUDY DESIGN

3.1 Overall Study Design

This is a multicenter, open-label, Phase II, randomized, controlled study to determine the efficacy, safety, and other indicators of clinical and biological activity of the combination of danvatirsen and pembrolizumab as first-line treatment for R/M HNSCC.

After providing informed consent, patients will be assessed for eligibility during the screening phase of the study. All patients must be willing and able to provide a formalin-fixed paraffin-embedded (FFPE) archival or fresh tumor sample collected during the screening period; a fresh biopsy is preferred if safe and feasible to obtain and consented to by the patient. Following the screening period, eligible patients will be randomized in a 2:1 ratio to danvatirsen + pembrolizumab or pembrolizumab monotherapy, respectively.

Patients will be stratified by CPS (CPS ≥ 1 and < 20 vs. CPS ≥ 20). An early assessment of response in patients with CPS ≥ 1 and < 20 will be performed and should the response rate in this subgroup not pass the minimum desired efficacy level, eligibility will be restricted to patients with CPS ≥ 20 .

Patients will receive treatment in 21-day cycles. Patients assigned to the pembrolizumab monotherapy arm will receive treatment until a criterion for discontinuation is met or a maximum of 24 months/34 cycles of treatment. Patients assigned to combination therapy will receive both treatments until a criterion for discontinuation is met or the patient has received a maximum of 24 months/34 cycles of pembrolizumab, after which they may remain on danvatirsen monotherapy.

As the combination of danvatirsen and pembrolizumab has not been evaluated previously, safety will be assessed on a continuous basis. A formal review of safety will be performed by the Safety Review Committee after the first 9 patients randomized have completed at least one cycle of the assigned study treatment. If accrual reaches 20 patients prior to availability of the safety results, accrual will be suspended. If the combination is deemed intolerable, further accrual will be halted.

[figure not shown]
A futility analysis will be conducted when ORR can be assessed for the first 39 patients, as described in more detail in [Section 9.2](#).

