4.1 Inclusion Criteria

To be eligible for study participation, all of the following inclusion criteria must be met:

1. Must have given written informed consent (signed and dated).
2. Patient is ≥ 18 years old or age of majority in the country in which they reside, whichever is higher.
3. Recurrent/metastatic histologically or cytologically proven squamous cell carcinoma of the head and neck that is considered incurable by local therapy. Eligible primary tumor locations are oropharynx, oral cavity, hypopharynx, and larynx.
4. Presence of measurable tumor per RECIST v1.1 criteria.
5. Detectable PD-L1 expression in tumor, defined as CPS ≥ 1 determined by a test approved by US FDA or national regulatory agency of the country in which the patient resides. A TPS value ≥ 30 may be used for initial eligibility however a CPS value must be obtained and reported utilizing a tissue sample obtained prior to the start of study treatment.
 - Examples of approved tests include PD-L1 IHC 22C3 pharmDx (Dako North America, Inc.); PD-L1 IHC 28-8 pharmDx (Dako North America, Inc.); Ventana PD-L1 (SP142) Assay (Ventana Medical Systems, Inc.); Ventana PD-L1 (SP263) Assay (Ventana Medical Systems, Inc)
6. Baseline fresh tumor biopsy or archival specimen. A fresh biopsy is preferred if safe and feasible to obtain and consented to by the patient (details provided in section on **Tissue Samples [Section 7.12.1]**).
7. ECOG performance status of 0 or 1.
8. Adequate organ function within 10 days of study treatment, including the following:
 - a. Absolute neutrophil count $\geq 1,500/\mu\text{L}$
 - b. Platelet count $\geq 100,000/\mu\text{L}$
 - c. Hemoglobin $\geq 9 \text{ g/dL}$ (may be with transfusion)
 - d. Serum creatinine within normal limits or, for patients with serum creatinine above institutional normal:
 - Creatinine clearance $\geq 45 \text{ mL/min}$
 - Creatine clearance can be calculated using an appropriate standard formula (e.g. Modification of Diet in Renal Disease equation [MDRD], Cockcroft-Gault formula, or another formula that is typically used at the

-
- institution) or can be obtained from a 24-hour urine collection. ([Appendix 2](#))
- e. Total bilirubin $\leq 1.5 \times$ upper limit of normal (ULN)

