Table 10: Operating Characteristics

Scenario	% ORR Control	% ORR Combination	Early Futility Stopping (%)	Claim Promising (%)	Average Sample Size
1	15	15	46.1	4.6	62
2	23	23	43.8	4.5	63
3	20	40	7.1	54.6	78
4	23	43	7.7	52.9	78
5	25	50	4.5	68.6	79
6	15	43	1.9	82.7	80

Abbreviation: ORR = objective response rate

Additional futility monitoring criteria will be taken into consideration for the subgroup of patients with CPS ≥ 1 and < 20 . Specifically, if no more than one patient achieves a response (confirmed or unconfirmed CR or PR within the first two scans) in the first 10 patients enrolled in the combination arm for this subgroup, there will be no further enrollment in this subgroup, and the study will continue to enroll in the CPS ≥ 20 subgroup, consistent with any guidance based on the monitoring criteria outlined in [Table 9](#). Additionally, accrual in the CPS ≥ 1 and < 20 subgroup will pause, if no responses have been achieved, but response data for the first 10 patients in that subgroup are not yet mature, defined as at least 2 scans assessed.

Considering the limited size of the CPS ≥ 1 and < 20 subgroup, the futility criteria were derived based on a single arm BOP2 design with the interim assessment after 10 patients, a final assessment of 27 patients (half of the intended size of the combination arm) testing a null hypothesis of 15% ORR (KEYNOTE-048 pembrolizumab monotherapy ORR for this subgroup ([Burtness et al 2022](#))) vs. an alternative hypothesis of 29% ORR (SCORES combination arm for this subgroup), at 1-sided 10% level with approximately 65% power.

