PFS is defined as the time from randomization to the first of either disease progression or death from any cause, where disease progression will be determined based on RECIST v1.1 criteria. A patient that starts a new anticancer therapy prior to disease progression will be censored at the date of last valid disease assessment prior to the start of the new anticancer therapy. Patients without documented disease progression or death will be censored at the last valid disease assessment date. Any patient without a valid disease assessment will be censored on the day of the first dose. PFS will be summarized using Kaplan-Meier methods and compared between the 2 groups using a stratified log rank test.

Sensitivity analyses for ORR, DOR, and PFS will be repeated with the requirement of confirmation of disease progression at least 4 weeks after an initial assessment of PD. Any unconfirmed disease progression assessment will not be counted as PD in these analyses.

OS is defined as the time from randomization to death from any cause. Patients without documentation of death as of the data cutoff will be censored at the last date the patient was known alive. OS will be summarized using Kaplan-Meier methods and compared between the 2 groups using a stratified log rank test.

All efficacy analyses will be performed for two key efficacy subgroups, which includes all patients with CPS ≥ 20 and CPS ≥ 50 . Additional subgroups of interest will be defined in the SAP.

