## 5.12.6 Subgroup Analyses

Subgroup analyses will be performed for the primary and secondary efficacy endpoints for the FAS population. This includes analysis for ORR, DOR, PFS, and OS. The following subgroups will be used.

- Baseline Combined Positive Score Category (CPS < 20, CPS >= 20)
- Sex at Birth (Male, Female)
- Age Group (< 65, >=65)
- ECOG PS (0, 1)
- HPV Status (Positive, Negative)
- Region (US, Non-US)

For subgroup analysis of PFS by Baseline CPS category, Baseline CPS category will be removed as a stratification factor from the Cox Proportional Hazard Model. All subgroup analyses are considered descriptive, and no hypothesis testing will be performed.

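### The SAP's baseline CPS classes leave out the 1-19 randomisation stratum, and its subgroup section drops the CPS ≥50 level that Protocol 9.7 sets for all efficacy analyses

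*SAP*

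**What the plan says.** **Eligibility and strata.** Protocol 4.1 requires: "Detectable PD-L1 expression in tumor, defined as CPS ≥ 1 determined by a test approved". Protocol 3.1 sets the groups: "Patients will be stratified by CPS (CPS ≥ 1 and < 20 vs. CPS ≥ 20". Protocol 9.2 gives the lower group its own stopping guidance: "Additional futility monitoring criteria will be taken into consideration for the subgroup of patients with CPS" at least 1 and below 20. Protocol 3.4 and SAP 4 and 5.3 say that CPS replaced ECOG status as the stratification factor by amendment, when the lower group was added.

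**Baseline table.** SAP 5.8, under Cancer History, summarises CPS as a score and then in classes: "Combined Positive Score (0, >= 20, 20 - 49, >=50".

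**Efficacy subgroups.** Protocol 9.7 states: "All efficacy analyses will be performed for two key efficacy subgroups, which includes all patients with CPS ≥ 20 and CPS ≥ 50". It leaves further subgroups to the SAP. SAP 5.12.6 has one CPS entry: "Baseline Combined Positive Score Category (CPS < 20, CPS >= 20". It introduces the subgroup analyses as covering primary and secondary efficacy endpoints, then adds: "This includes analysis for ORR, DOR, PFS, and OS". SAP 5.12.3 names CPS ≥20 and ≥50 for ORR and DOR only.

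**Declared changes.** SAP section 9 lists one change from the protocol, an earlier final analysis because the study ended early.

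**The concern.** There are two separate faults.

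The first is in a descriptive table. CPS is the current stratification factor, and Protocol 1.2 says it was chosen to learn whether higher PD-L1 expression goes with a higher response rate. A reader of a CPS ≥1 result will want the CPS mix in each arm. The planned classes offer a row that should be empty and none for the lower stratum.

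The second is a conflict between the documents. The protocol names CPS ≥50 as a key subgroup for all efficacy analyses, and the SAP's subgroup section has no such level. The SAP also disagrees with itself, because 5.12.3 needs ORR and DOR at CPS ≥50. If the SAP is programmed as written, PFS and OS results that the protocol promised will not be produced. Whether DCR and CR rate appear at CPS ≥50 will depend on the table shells. CR rate has some weight here, since Protocol 9.10.2 lets it support advancement when ORR falls short.

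**Working it through.** **1. The plan's own figures.** The point disputes no figure. As background, exact binomial enumeration of the Protocol Table 9 boundaries (13 and 26 patients at the interim, 27 and 54 at the end) gives these results against Table 10:

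| Quantity | Recomputed | Protocol Table 10 |
|---|---|---|
| Power at 15% v 43% | 82.6% | 82.7% |
| Claim promising at 15% v 15% | 4.5% | 4.6% |
| Early futility stop at 15% v 15% | 46.4% | 46.1% |

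None of these depends on how CPS is grouped in the tables.

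**2. Baseline classes.** Each whole-number score from 1 to 100 was set against the four classes in SAP 5.8.

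| CPS | Status in the trial | Class in SAP 5.8 |
|---|---|---|
| 0 | ineligible | 0 |
| 1-19 (19 scores) | eligible; lower stratum | none |
| 20-49 | eligible; upper stratum | ≥20 and 20-49 |
| 50 and over | eligible; upper stratum | ≥20 and ≥50 |

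The overlap above 20 does no harm if ≥20 is read as a subtotal. The gap at 1-19 remains.

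**3. Can the lower stratum be recovered?** For an arm of N patients:

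N − n(CPS ≥20) = n(CPS 1-19) + n(CPS missing).

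Subtraction gives the stratum size only if no CPS is missing. Protocol 4.1 allows initial eligibility on a Tumor Proportion Score (TPS), and SAP 5.3 assigns such patients to a stratum from TPS. CPS must still be obtained, but the table has no row to show whether it was. The CPS <20 efficacy subgroup is the other source. It is presented by planned treatment for the Full Analysis Set, whereas the baseline table is by actual treatment for the Safety Analysis Set.

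**4. CPS ≥50, endpoint by endpoint.**

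| Endpoint | Protocol 9.7 at CPS ≥50 | SAP at CPS ≥50 |
|---|---|---|
| ORR | yes | yes, 5.12.3 |
| DOR | yes | yes, 5.12.3 |
| PFS | yes | not specified |
| OS | yes | not specified |
| DCR | yes | not explicit; shares table 14.2.1.2 with ORR, levels not stated |
| CR rate | yes, as a secondary efficacy endpoint | not explicit; in no by-CPS table title |

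Two endpoints are kept, two are unspecified and two are left unclear.

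**The case against.** The strongest reply is that this is a drafting slip of small consequence, and much of that reply stands.

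- **The lower stratum is not lost.** SAP 4 and 5.3 define it, 5.12.6 analyses CPS <20, the log-rank and Cox analyses stratify by baseline CPS category, and the score itself is summarised and listed. A reader might infer that the SAP's CPS groupings as a whole fail to match the design, or that the lower stratum cannot be seen. The documents support neither. The fault is confined to one set of baseline classes.
- **DCR and CR rate may be carried by the ORR analysis.** SAP 5.12.2 tabulates every best-response category, 5.12.3 analyses all rates alike, and ORR and DCR share a by-CPS table. The table shells are not among the documents. It would be too strong to say that four endpoints have no CPS ≥50 analysis; the clear gap is PFS and OS.
- **The SAP matches the protocol's objectives table.** That table names only ORR and DOR for CPS ≥50. This may explain the omission, but Protocol 9.7 goes further and leaves only additional subgroups to the SAP.
- **Changes may be justified elsewhere.** Protocol section 9 says they will be described in the clinical study report. That is fair, but the SAP has its own section for changes, and it is silent on this one.
- **Protocol 9.7 does not name CPS 1-19.** This is correct. The case for a 1-19 baseline row rests on eligibility and stratification, not on 9.7.

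**Conclusion.** Both faults hold on the text. SAP 5.8 has a class that no eligible patient can occupy and no class for scores 1-19. SAP 5.12.6 omits the CPS ≥50 level that Protocol 9.7 sets for all efficacy analyses, which leaves PFS and OS there unspecified and DCR and CR rate not explicitly specified, without a declared change. SAP 5.12.6 and 5.12.7 make the subgroup and secondary analyses descriptive, so the primary test, alpha and power do not move.

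The number of patients affected at baseline is not known. A reader might take Protocol 9.2's "a final assessment of 27 patients (half of the intended size of the combination arm" and infer that half the trial falls in no class: 27/54 = 50%, or 27 × 3/2 = 40.5 of 81. That 27 is the final size assumed for a single-arm futility rule, not an expected enrolment share. If instead the stratum closed with 10 combination patients, 2:1 allocation would give 10 × 3/2 = 15 of 81 (19%). Both are assumptions. The stratum was added by amendment and the study ended early, so the true number could be lower. The fault stands at any number above zero.

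A reader might also infer that the SAP discards the top of a PD-L1 gradient that motivated the trial. The earlier danvatirsen-durvalumab results in Protocol 1.1.2 give CR rates of 11% to 13% at CPS ≥1 and 19% to 22% at CPS ≥20, and nothing at CPS ≥50. Response rate at CPS ≥50 is kept in any case.

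**What to change.** 1. In SAP 5.8, list CPS 1-19, 20-49 and ≥50, with ≥20 as a subtotal and a row for missing CPS. Drop the class 0.
2. In SAP 5.12.6, the by-CPS tables (14.2.1.2, 14.2.2.2.2 and 14.2.2.3.2) and the forest plots, add CPS ≥50 alongside <20 and ≥20 for all efficacy endpoints, and name DCR and CR rate. Alternatively, declare and justify the reduction from Protocol 9.7 in SAP section 9.

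SAP section 5 requires the SAP and shells to be approved before database lock, so the edit belongs before that point; afterwards it would need the addendum that section describes.

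The cost is SAP and shell edits and a few extra rows. Protocol 4.1 already requires a CPS value for each patient, so no new data are needed. The drawback is that the CPS ≥50 intervals will be wide, and the results stay descriptive.
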